5.1 INCLUSION CRITERIA

Participants are eligible to be included in the study only if all of the following criteria apply:

Age

I 01. Participant must be 18 to 60 years (inclusive) of age, at the time of signing the informed consent.

Type of participant and disease characteristics

I 01. Participants with a diagnosis of RRMS, SPMS (relapsing or non-relapsing), or primary progressive subtype according to the 2017 revision of the McDonald diagnostic criteria (SPMS diagnostic criteria according to [13] include an initial relapsing remitting disease course followed by progression with or without occasional relapses, minor remissions, and plateaus; progression denotes the continuous worsening of neurological impairment over at least 6 months).

I 02. Participants with an Expanded Disability Status Scale score of 2-6 inclusive at screening.

I 03. Participants who are either untreated or in the opinion of the Investigator are stable on an allowed DMT (interferons, glatiramer acetate, fumarates, or teriflunomide) for at least the past 3 months, AND not anticipated to require a change in MS treatment for the duration of Part A and Part B (through Week 96); in Part B changes in dose of allowed DMTs or transition to other allowed DMTs is permitted).

Weight

I 04. Participants with body weight ≥ 45 kg and body mass index (BMI) ≥ 18.0 kg/m².

Sex, contraceptive/barrier method, and pregnancy testing requirements

I 05. All

Contraceptive use by men and women should be consistent with local regulations regarding the methods of contraception for those participating in clinical studies.

a) Male participants

- Male participants are eligible to participate if they agree to the following during the study period and for at least 92 days following their last dose of IMP:
- Refrain from donating or cryopreserving sperm
Plus, either:
- Be abstinent from heterosexual intercourse as their preferred and usual lifestyle (abstinent on a long-term and persistent basis) and agree to remain abstinent

OR

- Must agree to use contraception/barrier (male condom) as detailed below:
A male condom and an additional highly contraceptive method as described in [Section 10.4.2](#) when having sexual intercourse with a woman of childbearing potential (WOCBP) who is not currently pregnant

b) Female participants

Female participants are eligible to participate if they are not pregnant or breastfeeding and 1 of the following conditions applies:

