3.3.1 Definition of endpoint(s)

Time to onset of 12-week CDP is defined as the time from randomization to the onset of an increase in EDSS score (defined as an increase of ≥ 1.0 point from the baseline EDSS score when the baseline score is ≤ 5.5 or an increase of ≥ 0.5 points from the baseline EDSS score when the baseline score is > 5.5) confirmed after a 12-week interval.

- The initial onset increase from baseline EDSS score must be observed at a routine quarterly visit.
- All intermediate EDSS scores (EDSS scores obtained after onset of progression and before the confirmatory assessment), if any, must maintain at least the minimum increase.
- Confirmatory EDSS assessment must be obtained at least 12 weeks after onset and at a routine quarterly visit.

Note: 12-week confirmation must be ≥ 78 days after onset. Given that visits are scheduled every 12 weeks with a time window of ± 3 days for conducting EDSS assessment in Part A, the minimum per protocol allowed time between 2 EDSS assessments scheduled 12 weeks apart is 78 days (12 weeks=84 days minus a 3-day window for each of the 2 visits, ie, $84-6 = 78$).

Time to onset of 24-week CDP is defined similarly with time to onset of 12-week CDP. The only difference is that for time to onset of 24-week CDP, the increase in EDSS score has to be confirmed over 24 weeks. Accordingly, the minimum per protocol allowed time between confirmation and onset is 154 days (6 months=24 weeks=168 days minus a 7-day for each of the 2 visits, ie, $168-14 = 154$). Both the initial onset and the confirmation must be observed at scheduled visits, and all intermediate EDSS scores if any must maintain at least the minimum increase.

If a participant dies due to MS, it will be considered a confirmed disability progression regardless of the baseline EDSS or the change in EDSS. The time to onset will be calculated as (date of EDSS assessment at a tentative onset of the event – date of randomization + 1) or (date of death – date of randomization + 1) if a tentative onset date does not exist. Death for other reasons than MS will not be considered a disability progression and the participant's event time will be censored at the date of last EDSS assessment.

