The 9-HPT is a brief, standardized, quantitative test of upper extremity function (lower bound: 10 sec; upper bound: 300 sec). Two consecutive trials with the dominant hand are immediately followed by two consecutive trials with the non-dominant hand. Let D_1 and D_2 be the time to complete the 9-HPT for the dominant hand for the two trials and let ND_1 and ND_2 be the time to complete the 9-HPT for the non-dominant hand for the two trials. The overall 9-HPT is calculated as:

$$9HPT = \frac{2}{\left(\frac{2}{D_1 + D_2}\right) + \left(\frac{2}{ND_1 + ND_2}\right)}$$

For a participant who could not complete the 9-HPT due to a “physical limitation”, the maximum time (300 sec) will be used. In case of missing data for other reason than inability to complete the test, missing data will be treated as follows:

- In case only 1 trial was done for a hand, the average of the two trials will be replaced by the time for the available trial.
- In case 9-HPT was assessed for only one hand, the overall 9-HPT will not be calculated and considered missing.

A higher value of overall 9-HPT is indicative of higher disability. In case of values below (above) the lower (upper) bound, the value will be set to the respective bound.

The T25-FW is a quantitative mobility and leg function performance test based on a timed 25-foot walk; time in seconds to walk 25 feet (lower bound: 2.2 sec; upper bound: 180 sec). For each assessment, 2 trials are performed. The score is the average of the times from the 2 trials (or single score if only 1 completed). For a participant who could not complete the 25-FW due to a “physical limitation”, the maximum time (180 sec) will be used. Missing values for other reasons will not be imputed. In case of values below (above) the lower (upper) bound, the value will be set to the respective bound. A higher value of T25-FW is indicative of higher disability.

Time to onset of 24-week CCDP, as assessed by composite endpoint EDSS-Plus (EDSS score, or T25-FW test, or 9-HPT), is to be confirmed over at least 24 weeks (3). Disability criteria for the individual components are defined as follows:

- Disability progression on the EDSS is defined as an increase of ≥ 1.0 point from the baseline EDSS score when the baseline score is ≤ 5.5 or an increase of ≥ 0.5 points from the baseline EDSS score when the baseline score is > 5.5 .
- Disability progression on the T25-FW test is defined as an increase (worsening) of $\geq 20\%$ from the baseline score.

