For analyzing the average number of new gadolinium- (Gd-) enhancing T1-hyperintense lesions per scan and annualized rate of new/enlarging T2-hyperintense lesions, the model will include the total count of the respective type of lesion across all scheduled MRI scans during the observation duration as the response variable, with treatment group, baseline lesions count and MS clinical subtype (RRMS, SPMS, or PPMS) as covariates. For Part B endpoints, the baseline lesions count will be replaced by the Week 48 lesions count. The offset variable will be the log transformed number of MRI scans during the observation duration for T1 lesions and log transformed observation duration for T2 lesions. The observation duration for Part A is from randomization to the last MRI scan on or prior to Week 48. The observation duration for Part B is from the end of Week 48 to last MRI scan on or prior to Week 96. The average number of lesions per scan (95% CI) for Gd-enhancing T1-hyperintense lesions and the annualized rate (95% CI) of new/enlarging T2-hyperintense lesions for each treatment group will be estimated from the model along with the relative risk (95% CI, p-value) for SAR443820 compared to placebo. The adjusted mean value

within treatment group is based on a sample size dependent weight within each categorical covariate (ie, weight by overall proportion of participants in each stratum or categorical factor, also called “population weight”).

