These time to event endpoints will be analyzed by a Cox proportional hazards model. The covariates included in the model are treatment group and MS clinical subtype (RRMS, SPMS, PPMS). The hazard ratio between treatment groups, its 95% confidence interval and the p-value will be estimated from this model with robust variance estimation (6). Comparison between treatment groups will also be assessed by a log-rank test stratified by MS clinical subtype (RRMS, SPMS, PPMS). Kaplan-Meier (KM) plots of the cumulative incidence rate will be provided by treatment group to depict the course of occurrence of event over time. The proportion of participants with events at given time points (eg, 12, 24, 36, 48, etc.) will be calculated using the KM estimates.

Continuous endpoints

Continuous endpoints include:

Part A

- Change from baseline in EDSS score at Week 48
- Change from baseline in 9-HPT at Week 48
- Change from baseline in T25-FW at Week 48
- Percent change from baseline in BVL at Week 48
- Change from baseline in the volume, number, and normalized T1 intensity of SELs at Weeks 12, 24, 36 and 48
- Change from baseline in the number of PRL at Weeks 12, 24, 36 and 48.

Part B

- Percent change from baseline in BVL at Week 96
- Change from baseline in the volume, number, and normalized T1 intensity of SELs to Week 96
- Change from baseline in the number of PRL at Week 96
- Change from baseline in EDSS at Week 96
- Change from baseline in 9-HPT at Week 96
- Change from baseline in T25-FW at Week 96
- Change from baseline in MSIS-29v2 physical and psychological domains score at Week 96
- Change from baseline in MSWS-12 at Week 96

Summary statistics including mean, standard deviation, median, interquartile range (Q1, Q3), minimum, and maximum will be provided for these continuous endpoints at scheduled visits. Only non-missing data will be included. For change/percent change from baseline, only participants with baseline and at least one post-baseline assessment will be summarized.

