Normalized T1 intensity of SELs may be explored using linear mixed model. The model will include the treatment group (SAR443820 or placebo), MS clinical subtype (RRMS, SPMS, or PPMS), time (from randomization to the date of MRI sample being collected), treatment-by-time interaction, baseline value of normalized T1 intensity of SELs as the fixed effects. Both intercept and the coefficient for time are assumed to have participant-level random effects and these two random effects are assumed to be independent.

The other continuous endpoints will be analyzed using a similar MMRM approach as described for the primary endpoint of Part A in [Section 3.2.2.1](#), except that the log-transformed baseline sNfL levels will be replaced by the baseline values of the corresponding endpoint. Appropriate transformation will be used if necessary (eg, log-transform). Plots of least squares means

(\pm standard error) over time will be provided. Plots of mean (\pm SE) and/or mean change (\pm SE) over time will also be provided.

No sensitivity or subgroup analyses will be conducted.

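### The Cox models for confirmed EDSS, 9-HPT and T25-FW worsening omit the matching baseline score: the analysis is valid, but prespecifying that score is a nearly free improvement

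*SAP*

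**What the plan says.** SAP 3.3.2, under the time-to-event endpoints, specifies one Cox model for all of them: 12-week confirmed EDSS, 9-HPT and T25-FW worsening in Part A, and the 24-week versions plus the EDSS-Plus composite (CCDP) in Part B. On the model terms it says: "The covariates included in the model are treatment group and MS clinical subtype (RRMS, SPMS, PPMS". A second test has the same limit: "Comparison between treatment groups will also be assessed by a log-rank test stratified by MS clinical subtype (RRMS, SPMS, PPMS".

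The events are defined against the participant's own baseline (SAP 3.3.1). For EDSS a rise of at least 1.0 is needed at a baseline of 5.5 or lower, but only 0.5 "points from the baseline EDSS score when the baseline score is" above 5.5. For the walk test, "Disability progression on the T25-FW test is defined as an increase (worsening) of" at least 20% from baseline, and the 9-HPT rule is the same. Protocol 5.1 admits "Participants with an Expanded Disability Status Scale score of 2-6 inclusive at screening", so both EDSS rules can apply within the trial.

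Elsewhere in SAP 3.3.2 baseline is used. The lesion-count models are fitted "with treatment group, baseline lesions count and MS clinical subtype (RRMS, SPMS, or PPMS) as covariates". The repeated-measures models of EDSS, 9-HPT and T25-FW follow the primary model, "except that the log-transformed baseline sNfL levels will be replaced by the baseline values of the corresponding endpoint". The section closes with "No sensitivity or subgroup analyses will be conducted". Whether that sentence covers all secondary endpoints or only the continuous ones, no baseline-adjusted Cox model is planned anywhere.

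**The concern.** The three scales are adjusted for baseline when analysed as change scores but not when analysed as time to worsening, and the SAP gives no reason. For EDSS, baseline also decides which event rule a participant falls under. Randomization is stratified by MS subtype only (SAP 1.1), so the arms may differ by chance in how many participants sit above 5.5.

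Time to 12-week confirmed EDSS progression is listed among the main secondary endpoints (Protocol 1.1). Within Part A, onset must fall at a quarterly visit and be confirmed at least 12 weeks later, so only Weeks 12, 24 and 36 can be onset visits. Events will probably be few. If baseline is prognostic, leaving it out gives away some precision and moves the estimated hazard ratio (HR) toward 1.

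**Working it through.** **Inputs from the documents.** 168 randomized 1:1 (84 per arm), 17% dropout, two-sided 0.05 for secondary endpoints (SAP 3.1), EDSS 2 to 6 at screening, onset visits as above. The documents give no event rate, target HR, power or prognostic strength of baseline for these endpoints. Every such value below is an assumption.

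**1. The plan's own figure.** 280 × (1 − 0.40) = 168, and 139 / (1 − 0.17) = 167.5, which rounds up to 168, so the headcount is consistent. The basis is sNfL precision: moving from a ratio of 0.70 to an upper limit of 0.90 needs a log half-width of ln 0.90 − ln 0.70 = 0.251. The SD is redacted, so this cannot be reproduced. It also says nothing about the Cox endpoints.

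**2. How strong the EDSS step could be.** If a fraction p has baseline above 5.5 and their hazard is k times higher, the log-HR per SD of that indicator is ln k × √(p(1 − p)). With k = 2 (assumed):
- p = 0.11: 0.693 × 0.313 = 0.22
- p = 0.25: 0.693 × 0.433 = 0.30

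Reaching 0.5 per SD would need k = exp(0.5/0.313) = 4.9 or exp(0.5/0.433) = 3.2. For 9-HPT and T25-FW the rule is the same 20% ratio for everyone. Baseline sets only the number of seconds, so the rule alone shows no dependence of risk on baseline.

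**3. Attenuation.** Let the hazard be proportional to exp(γx + ln HR × treatment), with x a standard-normal baseline score. The large-sample treatment-only Cox estimate b solves ∫[f₁ − (f₀ + f₁)S₁eᵇ/(S₀ + S₁eᵇ)]dt = 0, where f and S are the arm-specific event density and survival averaged over x. For placebo event rates of 10% to 30%:

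| γ per SD | true HR 0.50 becomes | true HR 0.70 becomes |
|---|---|---|
| 0.3 | 0.501–0.504 | 0.701–0.703 |
| 0.7 | 0.508–0.523 | 0.707–0.719 |
| 1.0 | 0.519–0.549 | 0.715–0.738 |

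**4. Power.** 1,000 simulated trials per scenario: N = 168, 17% dropout, onsets grouped to Weeks 12/24/36, subtype in both models, Efron ties, Wald test. Entries are power without baseline → with baseline.

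| placebo rate | true HR | γ = 0 | γ = 0.3 | γ = 0.7 |
|---|---|---|---|---|
| 20% | 0.50 | 33.8% → 33.8% | 33.9% → 34.2% | 32.5% → 36.1% |
| 20% | 0.70 | 15.1% → 15.2% | 13.0% → 13.4% | 13.0% → 16.0% |
| 10% | 0.50 | 12.1% → 12.3% | 12.4% → 12.0% | 13.3% → 14.3% |
| 10% | 0.70 | 5.9% → 6.2% | 7.6% → 7.8% | 5.0% → 5.3% |

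Mean events ran from about 12 to 27. The largest gain is 36.1 − 32.5 = 3.6 points. A separate simulation with stronger assumptions (true HR 0.40, γ 0.5 to 1.0, 18 to 36 events, 800 trials per scenario) gave gains of 0 to 7 points and type I error of 2.4% to 4.6%.

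**5. Scale.** Schoenfeld's power is Φ(|ln HR|√d/2 − 1.96) for d events. With 20 events it is 34% at HR 0.50 and 12% at HR 0.70. With 40 events it is 59% and 20%. The number of events matters far more than the covariate.

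**6. Chance imbalance.** Assume p = 0.15 above 5.5 and k = 2 to 3. One SD of the difference between arms is √(2 × 0.15 × 0.85/84) = 0.055. Split evenly around 0.15, this moves the unadjusted HR by a factor of 1.1775/1.1225 = 1.05 (k = 2) to 1.355/1.245 = 1.09 (k = 3). With 20 events the SE of the log HR is about 2/√20 = 0.45, so the shift is well inside sampling error.

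**Limits.** The simulations in step 4 used a normal covariate, model-based rather than the planned robust variance, and a non-prognostic subtype. Monte Carlo error is about 1.5 points on each power.

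**The case against.** The strongest defence is that nothing is broken. The Cox model adjusts for the randomization stratum and the log-rank test is stratified by it. The treatment-only HR is a legitimate marginal effect, and its distance from the conditional HR reflects non-collapsibility, not bias. That stands.

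A reader might infer more: that the omission certainly loses power, biases the result, or leaves all three event rules tied to baseline by construction. The documents do not support these readings. The losses require baseline to be prognostic beyond subtype, for which they give no figure. The threshold argument applies to EDSS only, and there it is two classes split at 5.5 within a narrow entry range.

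The SAP is also not uniform in using baseline: the relapse-rate model has treatment as its only covariate. With few events, a short covariate list is defensible. This tempers the inconsistency argument but does not explain why the same scales are treated differently within one section. It is also a reason to add only one term to each Part A model.

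Finally, a linear EDSS term does not reproduce a step at 5.5, so it corrects an imbalance there only in part. That is true. It still captures any general gradient in risk with baseline.

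**Conclusion.** The omission is real and is not made good elsewhere in the SAP. It is a minor point of efficiency and consistency, not of validity: the planned comparison is sound and type I error is not inflated.

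The size depends on an unknown. If baseline carries no information beyond subtype, nothing is lost. At 0.3 per SD, about what the EDSS step alone would give under the assumptions above, the HR moves by 0.001 to 0.004 and power changes by less than half a point, which is within simulation error. At 0.7 per SD the HR moves by about 0.007 to 0.023 and power by up to about 4 points. At 1.0 per SD the HR moves by up to about 0.05.

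It would be wrong to read low power on these endpoints as a result of the missing covariate. Few events cause it, and it remains after adjustment. The case for acting is that the remedy uses data already collected and costs almost nothing.

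**What to change.** Amend the time-to-event paragraph of SAP 3.3.2, before unblinding, so that each Cox model keeps treatment group and MS clinical subtype and adds the baseline of the measure that defines the event, with baseline as defined in SAP 3.1:

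- confirmed EDSS progression: baseline EDSS, continuous
- confirmed 9-HPT worsening: log baseline 9-HPT
- confirmed T25-FW worsening: log baseline T25-FW
- Part B composite: all three, since any of them can trigger the event

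In Part A add only the one matching term. The stratified log-rank test can stay as it is. If the sponsor prefers the present model, one sentence giving the reason would do.

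The cost is a wording change and one degree of freedom per single-measure model (three for the composite), with no new data. The HR becomes conditional on baseline rather than marginal, which the report should state. Timing matters because a covariate added after unblinding would look data-driven.

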1 INTRODUCTION

1.1 STUDY DESIGN

Study ACT16753 is a Phase 2, randomized, double-blind, placebo-controlled, 2 parallel-arm study evaluating the effect of SAR443820 on serum neurofilament light chain (sNfL) levels in participants with multiple sclerosis, followed by an open-label, long-term extension period.

The study consists of 2 parts (A and B) as follows:

Part A is a 48-week, double-blind, placebo-controlled part, preceded by a screening period of up to 4 weeks before Day 1.

- The screening period will be up to 4 weeks and is designed to evaluate suitability for participation in the study in terms of MS diagnosis, clinical status based on EDSS, and safety screening evaluations. No IMP will be administered in this period.
- The double-blind treatment period will have a total duration of 48 weeks for each participant and will include the following:
 - Participants will be randomized at 1:1 ratio to receive SAR443820 20 mg QD (n = 84) or matching placebo QD (n = 84).
 - Randomization will be stratified by MS clinical subtypes (ie, RRMS, SPMS, or PPMS) in order to ensure a balance between the treatment and placebo arms within each MS clinical subtype. Participants will attend in-clinic study assessments at baseline (Day 1) and Weeks 2, 6, 12, 24, 36, and 48.

All participants who successfully completed Part A will be offered to rollover to Part B.

Participants who discontinue IMP during Part A, or who choose not to enter Part B will have their early discontinuation or safety follow-up visit, respectively, up to 2 weeks after the last dose of IMP.

Part B is an open-label, long-term extension of Part A. Part B starts from the end of Part A (Week 48) and continues up to Week 96.

- The assignment of participants to study intervention in Part A will remain double-blinded during Part B unless there is medical need to unblind the study intervention assignment.
- All participants will receive 20 mg QD SAR443820 in Part B.
- Participants will attend in-clinic study assessments at Weeks 52, 72, and 96 (and Week 48 which is the last visit of Part A and first visit of Part B); Week 50, 54, 56, 58, 60, 62, 64, 66, 68, 70, 76, 80, 84, 88, 92 visits for liver chemistry only may be conducted at local labs where available.

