3 STATISTICAL ANALYSES

3.1 GENERAL CONSIDERATIONS

In general, continuous data will be summarized using the number of observations available, mean, standard deviation (SD), median, interquartile range (Q1, Q3), minimum, and maximum.

Categorical and ordinal data will be summarized using the count and percentage of participants.

Efficacy data will be analyzed in the randomized and treated population except the primary endpoint which will be analyzed in the mITT population, and safety data will be analyzed in the safety population, unless specified otherwise.

In Part A, baseline values are defined as follows. The baseline value of NfL is defined as the lower value of screening and Day 1 visits if the number of gd-enhancing T1 lesion at Day 1 is greater than zero, otherwise it will be the average values of the assessments on screening and Day 1 visits prior to the first dose of the study intervention. The baseline values of EDSS and PD biomarkers other than NfL are defined as the average of the screening and Day 1 visit values prior to the first dose of the study intervention. If one of the values for the above assessments at screening and Day 1 is missing, the non-missing value will be used as the baseline value. For the other efficacy and safety assessments, the baseline values are defined as the last available value before the first dose of the study intervention. For the C-SSRS, the baseline value will be the worst assessment between the past 6 months evaluation at screening and the since last visit evaluation on Day 1. For participants randomized but not treated, the baseline value is defined as the last available value before randomization. Unless otherwise indicated, 2-sided p-values and 95% confidence intervals [CI(s)] will be provided for efficacy assessment of treatment differences. Unless otherwise specified, analyses will be performed by initial intervention group, ie, placebo or SAR443820 20 mg QD (and overall for baseline and demographics characteristics).

In Part B, efficacy analyses will be conducted accumulatively according to the treatment group allocated by randomization in Part A (ie, placebo/SAR443820 20 mg QD versus SAR443820 20 mg QD/ SAR443820 20 mg QD). Baseline values defined above for Part A will be used as the baseline in the efficacy analyses for Part B, unless otherwise noted. Safety analyses in Part B are specified in [Section 3.6](#).

Observation period

The observation period for safety will be divided into 4 segments:

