4 SAMPLE SIZE DETERMINATION

Sample size calculations were performed to ensure reasonable accuracy for the estimation of the ratio of the SAR443820 arm sNfL geometric mean relative to the placebo arm sNfL geometric mean. The width (when a GMR of █ is observed, which corresponds to a 30% reduction relative to placebo) of the 2-sided 90% CI, using a coverage correction to ensure coverage probability of █%, is displayed for various sample sizes in [Table 7](#):

Table 7 - Sample size determination

N	Log-transformed data			Corresponding geometric mean ratio (GMR)					
	Difference in means	Standard deviation (SD)	90% confidence interval (CI) half width*	Lower limit	Upper limit	GMR	Lower limit	Upper limit	Total width (asymmetric)
█	█	█	█	█	█	█	█	█	█

(*): with a coverage probability (probability that the observed interval will be no longer than the specified width) of 90%.

For an observed █ reduction relative to placebo, a sample size of 168 participants (to account for an anticipated 17% dropout rate) will provide an upper limit below 0.90 (10% of reduction) for the 2-sided 90% CI, which is deemed sufficient.

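### The optional mixed model for SEL T1 intensity sets the intercept-slope correlation to zero, which can modestly misstate the standard error of the treatment slope

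*SAP*

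**What the plan says.** SAP 3.3.2, under continuous endpoints, lists this secondary outcome for Part A: "Change from baseline in the volume, number, and normalized T1 intensity of SELs at Weeks 12, 24, 36 and 48". The planned reporting is descriptive summary statistics at scheduled visits. The SAP then adds an option: "Normalized T1 intensity of SELs may be explored using linear mixed model".

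The fixed effects are treatment, MS clinical subtype, time, "treatment-by-time interaction, baseline value of normalized T1 intensity of SELs as the fixed effects". Time runs from randomization to the scan date. Intercept and slope vary between participants, and "these two random effects are assumed to be independent". No reason is given for that assumption.

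The section does not say which contrast will be reported. SAP 3.1 supplies the default: "2-sided p-values and 95% confidence intervals [CI(s)] will be provided for efficacy assessment of treatment differences".

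Other models in the SAP have protection that this one lacks:
- The primary MMRM (SAP 3.2.2.1) uses an unstructured covariance with an ordered list of fallbacks.
- The negative binomial and Cox models (SAP 3.3.2) use robust variance.
- SAP 3.3.2 rules out sensitivity analyses for secondary endpoints.

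**The concern.** Independence of intercept and slope is an assumption about one point on the time axis, here randomization. The Part A scans that feed the model lie at Weeks 12 to 48, so the constraint is imposed at the edge of the data. Under independence the variance between participants can only grow from time zero. If participants with a high starting intensity tend to change in a different direction or at a different rate, that is untrue, and the fit compensates by distorting the slope and residual variances.

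The treatment-by-time slope is the natural quantity to read from this model. Its standard error is built from those two variances, so its interval and p-value are at stake. The point estimate is not.

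**Working it through.** The SAP states no standard error, power or variance component for this model, so it has no figure to reproduce.

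**Inputs from the documents.** Scans at Weeks 12, 24, 36 and 48; 84 participants per arm (SAP 1.1); 17% dropout (SAP 4); two-sided 95% intervals (SAP 3.1). Evaluable number: 168 × 0.83 = 139.4, about 70 per arm.

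**Assumed inputs.** Intercept SD, slope SD per 48 weeks and residual SD each between 0.25 and 1; correlation ρ between -0.8 and +0.8.

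**True standard error.** In 48-week units the visits are 0.25, 0.50, 0.75 and 1.00, with mean 0.625. So Sxx = 2 × (0.125² + 0.375²) = 0.3125. With complete balanced data and no baseline term, the treatment slope has

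SE = √[2(σ₁² + σₑ²/Sxx)/n],

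where σ₁ is the slope SD, σₑ the residual SD and n the number per arm. This does not contain ρ. For SDs 1, 1 and 0.5 and n = 70: √[2 × (1 + 0.25/0.3125)/70] = √(3.6/70) = 0.227.

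**Reported standard error under independence.** In large samples the constrained fit converges to the matrix Vm that minimises log|Vm| + tr(Vm⁻¹V), where V is the true covariance and Vm has zero intercept-slope covariance. Its fitted variances replace σ₁² and σₑ² in the formula above. The ratio of reported to true SE, with no baseline covariate, is:

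| ρ | Ratio over the assumed SDs |
|---|---|
| -0.8 | 0.80-0.98 |
| -0.5 | 0.89-0.98 |
| -0.2 | 0.96-0.99 |
| 0 | 1.00 |
| +0.2 | 1.01-1.03 |
| +0.5 | 1.02-1.07 |
| +0.8 | 1.03-1.10 |

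With 17% monotone dropout the overall range is 0.81-1.11. With a Week 96 scan added (four sets of SDs) it is 0.82-1.08.

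**Adding the specified baseline covariate.** The baseline value is measured at time zero and absorbs part of the intercept. Over seven assumed sets of SDs, with ρ defined on the participants' underlying intercept and slope:

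| ρ | No baseline term, or ρ defined after baseline adjustment | Baseline term included |
|---|---|---|
| -0.6 | 0.86-0.93 | 0.92-0.97 |
| +0.6 | 1.05-1.08 | 0.99-1.04 |

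Other SDs within the assumed ranges bring the ratio closer to 1.

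**Coverage of a nominal 95% interval.** 2Φ(1.96k) - 1 for ratio k gives 92.9% at 0.92, 94.3% at 0.97, 90.8% at 0.86 and 93.2% at 0.93. On the other side it gives 94.8% at 0.99, 95.8% at 1.04, 96.0% at 1.05 and 96.6% at 1.08.

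**Finite-sample check.** REML, 70 per arm, visit jitter of ±3 days, no baseline term, SDs 1, 1 and 0.5, just under 1,000 runs per row:

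| ρ | Covariance | Empirical SD | Mean SE | Ratio | Rejection at 5% |
|---|---|---|---|---|---|
| -0.5 | independent | 0.227 | 0.202 | 0.889 | 7.5% |
| -0.5 | unstructured | 0.227 | 0.226 | 0.997 | 4.4% |
| +0.5 | independent | 0.222 | 0.242 | 1.087 | 3.7% |
| +0.5 | unstructured | 0.222 | 0.226 | 1.015 | 4.6% |

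The empirical SD agrees with the formula (0.227) and is the same under both structures, so only the reported SE changes. With slope SD 0.5 and ρ = +0.5 the simulated ratios were 1.00 (independent) and 0.95 (unstructured), both about 5% below the large-sample values. The gap between the two structures (0.183 against 0.174) still agrees with theory.

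**The case against.** The strongest reply is that little depends on this model. It is optional, it concerns one MRI measure among many secondary endpoints, the committed analysis of that measure is descriptive, and no multiplicity-controlled claim rests on it. All of that stands and sets the severity.

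The second reply is that a calculation without the baseline covariate exaggerates the problem. That largely stands: with the covariate, the worst understatement at -0.6 falls from about 14% to about 8%. The larger figure survives only if a correlation of -0.6 is assumed for effects already adjusted for baseline, and nothing in the documents argues for one that strong.

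A reader might also infer that the standard error is wrong whenever the effects are correlated. That does not follow. With balanced complete data and time centred at the mean visit, the ratio was exactly 1.00 at every correlation tested. With a residual SD of 0.03 or less against an intercept SD of 1 and a slope SD of 0.5, it stayed within 0.2% of 1 for correlations up to ±0.5. Nor do the documents support calling the test anti-conservative: they give no sign for the correlation, and a positive one usually makes the interval slightly too wide.

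None of these replies supplies a reason for the independence assumption itself.

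**Conclusion.** The point holds as a minor one. With time counted from randomization and no robust variance, the independence constraint can misstate the standard error of the treatment-by-time slope for SEL T1 intensity. Under the assumed components, a correlation of -0.6 understates it by about 3-8% with the baseline covariate included, or 7-14% if the correlation applies after baseline adjustment. At +0.6 the error runs from 1% too small to 4% too large, or 5-8% too large.

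These sizes rest on assumed variance components. Neither direction nor size in this trial can be read from the documents. The slope estimate is essentially unchanged, and the primary sNfL analysis, which has its own unstructured covariance, is untouched.

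**What to change.** In SAP 3.3.2, replace the independence statement with a random intercept and slope that have an unstructured two-by-two covariance. If that model does not converge, fall back to independent effects with an empirical (robust) standard error, and report which model was used. This follows the approach the SAP already takes for the primary MMRM: the general structure first, simpler ones only if needed.

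The cost is one extra covariance parameter and a small risk of non-convergence, which the fallback covers. In the simulated scenarios the change brought no loss of precision in the slope estimate.
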